A Comparative Study of Retrograde Insertion of a Ureteral Catheter or Not in Total Tubeless Percutaneous Nephrolithotomy

NCT number: Waiting for the number

Version number: V3.0

Release date: October 8, 2022

1. **Title:** A Comparative Study of Retrograde Ureteral Catheter Insertion or Not in Total Tubeless Percutaneous Nephrolithotomy
2. **Registered:** It is intended to be registered in the International Clinical Trial Registry (www.clinicaltrials.gov/).
3. **Trial protocol version and date:** Version3.0/October 8, 2022
4. **Funding Project:** This study was supported by the Clinical Research Project of University of South China (USCKF201902K01), and the Hunan Provincial Clinical Medical Technology Innovation Guiding Project (2020SK51801).
5. **Study participants and responsibilities:** one experienced associate chief urologist performed the surgery, and at least 3-5 researchers participated in data collection and analysis.
6. **The research background and theory:** Total tubeless Percutaneous nephrolithotomy (PCNL) is a modified surgical method of PCNL surgery, that is, there is no indwelling nephrostomy tube and double-J tube during PCNL surgery. Compared with traditional PCNL surgery, it has the advantages of reducing pain, shortening operation time, and reducing operation cost. Since this procedure was first performed in 2004, several randomized clinical studies have verified the safety and efficacy of total tubeless PCNL. With the continuous development of minimally invasive surgery, since the successful implementation of tubeless PCNL in 1997, several randomized controlled clinical studies have verified the safety and feasibility of total tubeless PCNL surgery. With the continuous update of ultrasound equipment and the continuous progress of physician puncture technology, the application of ultrasound guided PCNL surgery is more and more popular. Moreover, ultrasound-guided percutaneous renal aspiration is increasingly independent of retrograde pyelography or artificial hydronephrosis. Therefore, PCNL without reverse insertion of a ureteral catheter has been attempted, especially when patients with severe rheumatoid arthritis or hip ankylosis are clinically encountered, and the lithotomy position is not possible. Passive PCNL without

reverse insertion of ureteral catheter has been successfully performed.

Therefore, it is theoretically feasible to carry out total tubeless PCNL without reverse insertion of a ureteral catheter for patients with unobstructed urinary drainage.

7. **Study objective:** The purpose of this study was to evaluate whether without retrograde ureteral catheterization is appropriate for total tubeless PCNL.
8. **Experimental design:** Parallel group design, a total of 2 groups (total tubeless PCNL group without reverse insertion of a ureteral catheter and conventional total tubeless PCNL group) were allocated according to 1:1 or approximately 1:1 for exploratory study.
9. **Study site:** Single-center study, conducted in the Department of Urology, The First Affiliated Hospital of the University of South China.
10. **Inclusion and exclusion criteria:** Inclusion criteria: (1) patients with kidney stones who met the indications for PCNL surgery; (2) the maximum diameter is less than 35mm; (3) the width of hydronephrosis effusion was less than 25mm. exclusion criteria :(1) patients with infectious calculi confirmed by preoperative CT examination and blood biochemical indexes; (2) Patients with severe cardiac and pulmonary insufficiency, coagulation dysfunction and other obvious surgical contraindications; (3) Patients with previous history of PCNL surgery on the affected side or nephrotomy; (4) Patients with indwelling double J tube or nephrostomy tube before operation; (5) Patients with renal trauma or congenital anomalies of urinary system.
11. **Intervention measures:** a. Total tubeless PCNL without reverse insertion of a ureteral catheter and conventional total tubeless PCNL were performed according to the group, and the same deputy chief physician of urology performed the operation according to the random group; B. Symptomatic treatment of patients during perioperative period is allowed, including antiinfection, analgesia, etc.

Total tubeless PCNL without reverse insertion of a ureteral

catheter implementation process: endotracheal intubation in patients with general anesthesia, prone position after detaching urethral catheter, used in ultrasound guided puncture needle percutaneous renal biopsy to appropriate calyces, under the direct observation of needle in the renal collecting system, using fascia dilator under guide wire step by step coaxial expansion of percutaneous renal channel to 16 Fr or 18 Fr. A rigid nephroscope was inserted and the stone was broken by holmium laser. The crushed stones were removed from the body using constant flow perfusion during stone crushing and stone removal. After checking that there was no residual "visible stone", the puncture sheath was slowly withdrawn, the skin-kidney channel was checked for active bleeding, and the skin incision was closed with suture.

[figure not shown]
The implementation process of conventional total tubeless PCNL:

Endotracheal intubation in patients with general anesthesia, patients were placed in a lithotomy position, and ureteral catheter was inserted reversely under transurethral ureteroscopy and fixed on the urinary catheter. Then, the patients were moved to a prone position and were disinfected again, under the guidance of ultrasound in establishing a channel process and stone removal process was the same as that in total tubeless PCNL without reverse insertion of a ureteral catheter, after inspection without the "visible" stone of residual, The puncture sheath was slowly withdrawn, the passage was checked for active bleeding, and the skin incision was closed with suture.

- 12. Outcome indicators:** The primary end point was the rate of postoperative complications, Observation indexes including postoperative fever, inflammation index change (postoperative blood leukocytes and neutrophils ratio changes value), hemorrhage (postoperative hemoglobin change value, red blood cell pressure change value and the incidence of renal subcapsular hematoma), kidney damage (postoperative serum creatinine change value),

pain (postoperative VAS pain score, non-steroidal anti-inflammatory analgesic and opioids Rate) and the incidence of pleural effusion. Secondary end points included stone free rate, operation time, postoperative hospital stay, and hospital costs.

13. Study flow charts

14. **Sample size:** a total of 100 subjects are expected to be included (50 in each group).

15. **Recruitment of study subjects:** Recruiting research subjects were conducted by a researcher in the Urology Clinic of the First Affiliated Hospital of the University of South China.

16. **Allocation sequence generation and implementation method:** A researcher was assigned to the group by random number method (odd number represents the conventional tubeless PCNL, and even number represents the total tubeless PCNL without reverse insertion of a ureteral catheter), which took place in the operating room.

17. **Blinding method:** single-blind, the enrolled patients were only told that they could receive either of the two surgical procedures, and the specific surgical method was determined by random number table method after entering the operating room.
18. **Data collection.** All data to be measured: 1. Demographic data, stone characteristics, and preoperative baseline data, including the proportion of gender, age, body mass index (BMI) and basic diseases distribution, location, stones, stone maximum cross-sectional area, the width of hydronephrosis, preoperative hemoglobin, Preoperative hematocrit, preoperative blood leukocyte count, preoperative blood neutrophils ratio, preoperative serum creatinine, urine leucocyte, site of puncture and operation laterality, 2. The primary end point of this study was the rate of postoperative complications, compared according to the modified Clavien-Dindo complication grading system. Observation indexes including postoperative fever, inflammation index change (postoperative blood leukocytes and neutrophils ratio changes value), hemorrhage (value changes of postoperative hemoglobin, red blood cell pressure change value and the incidence of renal subcapsular hematoma), kidney damage (postoperative serum creatinine values change), pain (VAS pain score, non-steroidal anti-inflammatory analgesic, and opioids demand rate) and the incidence of pleural effusion. Secondary end points included stone clearance rate, operation duration, postoperative hospital stay, and hospital costs. 3. Follow-up data included pain, hematuria, fever and readmission for 3 months after operation. Three researchers conducted data statistics respectively and obtained three original data, which were finally averaged.
19. **Statistical analysis plan:** SPSS26.0 version statistical software was used for analysis. Measurement data were expressed as mean \pm standard deviation ($\bar{X} \pm S$), and Student's t-test was used for intergroup comparisons. The counting data were expressed as frequency and percentage, and the chi-squared or

Fisher's exact probability test was used for intergroup comparisons. The ranksum test was used for grade data. $P < 0.05$ was considered statistically significant.

20. **Approval of informed consent and ethics:** This study followed the ethical standards set out in the Declaration of Helsinki. Informed consent was obtained and signed by all enrolled patients to undergo the two surgical procedures (total tubeless PCNL without reverse insertion of a ureteral catheter and conventional total tubeless PCNL) and to collect and use the medical information and biological samples for the study.
21. **Confidentiality measures:** The identifiable information of the subjects is replaced by irrelevant character sequences to ensure that the relevant personal information of the subjects will not be disclosed in any form.
22. **Declaration of Interest:** There is no conflict of interest between the investigator and the organization.
23. **Data Acquisition:** When proper editing or review requirements are met, the study data may be obtained from the study manager after the study is completed.

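### The protocol asks whether leaving out the catheter is appropriate, but its only criterion is P<0.05 on difference tests, which at 50 per arm can support that only if omission proves superior

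*Protocol*

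**What the plan says.** - **Section 7 (Study objective):** "The purpose of this study was to evaluate whether without retrograde ureteral catheterization is appropriate for total tubeless PCNL". The protocol does not define the word appropriate, and it names no superiority, non-inferiority or equivalence hypothesis.
- **Section 8 (Experimental design):** the two groups "were allocated according to 1:1 or approximately 1:1 for exploratory study".
- **Section 12 (Outcome indicators):** "The primary end point was the rate of postoperative complications". Section 18 adds that it is compared by the modified Clavien-Dindo grading.
- **Section 14 (Sample size):** "a total of 100 subjects are expected to be included (50 in each group"), with no expected rates, effect size, power or margin.
- **Section 19 (Statistical analysis plan):** a t-test for measurements and, for counts, chi-squared or Fisher: "Fisher's exact probability test was used for intergroup comparisons". For ordered categories: "The ranksum test was used for grade data". The significance threshold is P<0.05, with sidedness unstated. Counts are also to be described as frequencies and percentages. No confidence interval is mentioned.

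**The concern.** The experimental operation drops a step of the conventional one, and the primary endpoint measures harm. On those terms, asking whether omission is appropriate most naturally means asking whether it adds an unacceptable number of complications. A test for a difference answers another question. If it is significant in favour of omission, the objective is supported; if it is significant against, the objective is refuted. If P≥0.05, the test says nothing about acceptability, because failing to find a difference is not evidence that there is none. The protocol does not say how it would read that result.

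A small trial with P≥0.05 could then be taken as support for omitting the catheter while a sizeable excess of complications remains possible. Nothing in the protocol commits the authors to reporting how large that excess could be.

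**Working it through.** There is no stated sample-size calculation to reproduce. The check asks what section 19's criterion can tell us at the section 14 sample size.

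**Inputs.** From the protocol: n = 50 per arm (section 14), chi-squared or Fisher and P<0.05 (section 19), complication rate as primary endpoint (section 12). Assumed: two-sided tests, and a conventional-arm rate of 10% to 30%, because the protocol gives none.

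**1. Power against a true excess.** Power is the sum, over all pairs of counts (x, y) with P<0.05, of Bin(x; 50, p₁) × Bin(y; 50, p₂). This is exact enumeration, with chi-squared uncorrected.

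| Conventional v no catheter | Chi-squared | Fisher |
|---|---|---|
| 10% v 20% | 0.303 | 0.195 |
| 20% v 30% | 0.212 | 0.155 |
| 30% v 40% | 0.180 | 0.132 |
| 20% v 40% | 0.595 | 0.515 |
| 30% v 60% | 0.876 | 0.829 |

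If omission truly adds 10 points, the result is non-significant with probability between 1 − 0.303 = 0.70 and 1 − 0.132 = 0.87.

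**2. Largest observed excess that is still non-significant.** Worked case, 5/50 v 12/50: the pooled rate is 17/100 = 0.17, and z = 0.14 / √(0.17 × 0.83 × 2/50) = 0.14 / 0.0751 = 1.86, so P = 0.062.

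The Newcombe interval combines the Wilson limits of each arm, which are 0.0435 to 0.2136 for 5/50 and 0.1430 to 0.3741 for 12/50:
- Lower: 0.14 − √[(0.24 − 0.1430)² + (0.2136 − 0.10)²] = −0.009
- Upper: 0.14 + √[(0.3741 − 0.24)² + (0.10 − 0.0435)²] = 0.286

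| Conventional | Largest non-significant, chi-squared | 95% Newcombe CI (points) | Largest non-significant, Fisher |
|---|---|---|---|
| 5/50 | 12/50 (+14 points), P=0.062 | −0.9 to 28.6 | 13/50 (+16 points), P=0.066 |
| 10/50 | 18/50 (+16 points), P=0.075 | −1.6 to 32.4 | 19/50 (+18 points), P=0.077 |
| 15/50 | 24/50 (+18 points), P=0.065 | −1.1 to 35.3 | 25/50 (+20 points), P=0.066 |

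**3. Identical observed rates.** At 5/50 in both arms the half-width is √[(0.2136 − 0.10)² + (0.10 − 0.0435)²] = 0.127. The same formula gives ±12.7, ±15.7 and ±17.5 points at observed rates of 10%, 20% and 30%.

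**4. Limits of the claim.** Not every doubling would be missed. With chi-squared, an observed 8/50 v 16/50 is non-significant (P=0.061) but 9/50 v 18/50 is significant (P=0.043). With Fisher, 9/50 v 18/50 is non-significant (P=0.070) but 10/50 v 20/50 is significant (P=0.049). An observed doubling therefore escapes only up to a conventional rate of 16% (chi-squared) or 18% (Fisher). Power for a true doubling from 30% exceeds 80% with either test.

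**The case against.** **The frame is supplied by the reader.** The protocol never defines appropriate and never says that P≥0.05 will be taken as support. That is correct, and the point is not that the authors have declared such a reading. It is that the one inferential rule they fix cannot deliver the stated objective unless omission proves superior.

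**The study is exploratory and has many outcomes.** An exploratory trial needs no confirmatory decision rule, and appropriateness could be judged over the whole profile, including stone clearance, operation time, stay and cost. The label does lower the seriousness. But it argues for estimation, while section 19's only inference is testing, and gains on secondary endpoints would not show that the complication risk is acceptable.

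**Intervals and interpretation are often left to a separate plan.** Reported frequencies and percentages would also let a reader compute an interval. Both are true. Yet section 19 is itself headed as the statistical analysis plan and does fix a criterion; the mismatch with section 7 lies in what is written.

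**The primary comparison might be ordinal.** Section 18 refers to Clavien-Dindo grades, and section 19 assigns the rank-sum test to graded data. The endpoint is worded as a rate, so two-proportion figures are a fair basis. A rank-sum comparison would have the same logical defect, but these magnitudes would not carry over exactly.

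**Rates and effect size are assumed.** They are, which is why ranges are shown. The logical point does not depend on them.

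**Conclusion.** The concern holds. The difference tests in section 19 do not match the objective in section 7: apart from significant superiority of omission on complications, no result under the stated criterion can establish that omission is appropriate. With 50 per arm and an assumed conventional rate of 10% to 30%, a true 10-point excess would go undetected in about 70% to 87% of trials. Observed excesses of 14 to 20 points can still be non-significant, depending on the rate and the test. These figures assume two-sided testing and a binary primary comparison. This should be fixed, and the improvement is cheap; the exploratory label keeps it from being more serious.

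**What to change.** 1. **Section 7:** word the objective as estimating the difference in complication rate without versus with the catheter.
2. **Section 19:** make the primary result the risk difference (no catheter minus conventional) with a two-sided 95% score-type confidence interval, for example Newcombe. Report its upper limit as the largest excess risk not excluded, and state that P≥0.05 will not be taken as evidence that omission is appropriate.

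A non-inferiority margin is optional. It would need clinical agreement and may be out of reach with 50 per arm. If both true rates are 10%, 20% or 30%, the chance that the upper Newcombe limit falls below an illustrative 10 points is 34%, 23% or 20%; for 15 points it is 64%, 47% or 39%. These margins only show the scale and are not proposals.

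**Cost:** wording in two sections and one interval calculation, with no extra patients or data. The price is a more modest conclusion.

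### Blinding is defined for the patient only, although the primary endpoint depends on staff grading complications and detecting hematoma and effusion

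*Protocol*

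**What the plan says.** Section 17 (Blinding method) describes the trial as "single-blind, the enrolled patients were only told that they could receive either of the two surgical procedures". It adds that the procedure is fixed by random number once the patient is in the operating room. It says nothing about the people who collect, grade or analyse outcomes, and neither does any other section.

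Section 12 (Outcome indicators) states: "The primary end point was the rate of postoperative complications". Section 18 (Data collection) adds that this rate is "compared according to the modified Clavien-Dindo complication grading system". No grader is named. The observation indexes listed with it include laboratory changes, fever, subcapsular hematoma and "pain (VAS pain score, non-steroidal anti-inflammatory analgesic, and opioids demand rate) and the incidence of pleural effusion".

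On staffing, section 5 gives one operating urologist and says that "at least 3-5 researchers participated in data collection and analysis". Section 18 says: "Three researchers conducted data statistics respectively and obtained three original data, which were finally averaged". Section 16 has a researcher carry out the allocation in the operating room. Section 11 says of care around the operation: "Symptomatic treatment of patients during perioperative period is allowed, including antiinfection, analgesia, etc".

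**The concern.** The surgeon cannot be masked in this comparison, but the person who decides whether an event is a complication, and of what grade, can be. Minor Clavien-Dindo grades often turn on judgement, and so may the call that a small hematoma or effusion is present. If whoever makes these calls knows the arm, the recorded rates can separate, or be drawn together, with no true change in outcome.

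Both directions matter here. The objective in section 7 is to judge whether leaving out the catheter is appropriate. Lenient grading in the new-technique arm could hide a harm, and strict grading in one arm could create a difference that is not there.

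The one safeguard in section 18, averaging three data sets, works against random reading error. If the three researchers lean the same way because they all know the allocation, the average leans that way too.

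**Working it through.** **Which parts of the endpoint are exposed**

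- Clavien-Dindo grade: assigned by staff, grader not named. Exposed.
- Subcapsular hematoma and pleural effusion: detected by staff. Exposed.
- Use of non-steroidal and opioid analgesics: treatment is discretionary under section 11. Exposed when it is given, not when the chart is read afterwards.
- Hemoglobin, hematocrit, leukocyte, neutrophil and creatinine changes: laboratory values. Hardly exposed.
- VAS pain: normally scored by the patient, who is the one party that section 17 describes as blinded. Not a good example of assessor bias.

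Masked grading from records would therefore act mainly on the first two items.

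**Illustration of size**

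There is no planned figure to reproduce: section 14 gives 100 patients, 50 per group, without an event rate, effect size or power.

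Inputs from the protocol: n = 50 per arm (section 14); significance at P < 0.05, and chi-squared or Fisher's exact test for counts (section 19).

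Inputs assumed: a two-sided test; a true complication rate of 15% in both arms; misgrading that raises the recorded rate in one arm by 5 or 10 percentage points. In patients this is 0.05 × 50 = 2.5 or 0.10 × 50 = 5 extra recorded events on average.

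Let x1 and x2 be the recorded events per arm, p1 and p2 the recorded rates, and p̄ = (x1 + x2)/100. The uncorrected chi-squared test rejects when

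|x1 − x2|/50 ÷ √(p̄(1 − p̄) × 2/50) > 1.96.

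The rejection probability is the sum, over all pairs (x1, x2) that reject, of Bin(x1; 50, p1) × Bin(x2; 50, p2). For Fisher's test the same sum runs over pairs with exact P < 0.05.

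| Recorded rates | Chi-squared | Fisher |
|---|---|---|
| 15% v 15% | 5.5% | 2.4% |
| 15% v 20% | 10.6% | 6.0% |
| 15% v 25% | 24.4% | 17.2% |

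The same calculation at other assumed true rates, for drifts of 0, 5 and 10 points:

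| True rate | Chi-squared | Fisher |
|---|---|---|
| 10% | 5%, 12%, 30% | 2%, 6%, 19% |
| 20% | 5%, 9%, 21% | 3%, 6%, 16% |
| 30% | 5%, 8%, 18% | 3%, 5%, 13% |

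Within this range, a 5-point drift takes chi-squared to 8–12% and Fisher to 5–6%. A 10-point drift takes them to 18–30% and 13–19%.

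**Feasibility from the protocol's own text**

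Section 11 describes channel creation and stone removal as the same in both arms, with the same sheath withdrawal and skin closure, so the wound need not reveal the arm. The ureteral catheter could. In the conventional arm it is fixed to the urinary catheter, and no removal time is stated. Grading away from the bedside, from redacted records, reduces that problem.

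**The case against.** The strongest reply is that the protocol is silent rather than wrong. A reader might infer from section 17 that the researchers know the arm. The text does not say so: it describes what patients are told and stops. That stands, and the point is therefore that the masked roles are not fixed, not that assessors are known to be unmasked.

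A reader might also infer that most of the primary endpoint is open to assessor bias. It is not: the laboratory changes and the VAS score largely escape it, as set out in the working.

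A third tempting reading is that masking needs no extra staff. Sections 5 and 18 make this plausible but do not establish it. The researchers who recruit (section 15) and allocate (section 16) may be among the three who handle the data. If only three researchers exist, they could not all be both separate from allocation and masked. Section 18 also does not say that the three grade complications.

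A fourth is that the lack of masking for the analyst is a defect. Coding the arms for analysis may be left to the statistical analysis plan, which is not at hand, so no finding rests on it.

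Finally, the drift is hypothetical, a 10-point drift means about five wrongly recorded patients among 50, and section 8 calls the study exploratory. All of this tempers the false-positive argument. None of it answers the fact that a declared design feature leaves the judged part of the primary endpoint unprotected when protection is cheap.

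**Conclusion.** The concern holds in a limited form. Section 17 fixes a single-blind design that describes the patient only, and nothing in the protocol masks whoever grades Clavien-Dindo complications or calls hematoma and effusion. Who is masked when the primary endpoint is assessed is a design matter for the protocol, so this is more than a detail left for later.

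The rejection rates in the working show what misgrading of two to five patients in one arm could do. They rest on an assumed true rate, an assumed drift and a two-sided test. They are not estimates of bias in this trial and do not show that any bias will occur.

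The change is worth making before grading begins. It is a moderate point: it alters no treatment, sample size or endpoint.

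**What to change.** In sections 17 and 18, state that Clavien-Dindo grading and the reading of subcapsular hematoma and pleural effusion are done by data researchers who took no part in randomisation or surgery, from records and images with the operation note and allocation withheld. Name these roles, and state that they do not overlap with the researcher who allocates under section 16. Coding the arms for the analyst is an optional addition.

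Cost: some work to redact records and keep roles apart, and possibly one more person if the existing researchers overlap with those who allocate.

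Limits: masking may be incomplete where chart entries mention the ureteral catheter. It also does not remove bias already present in bedside recording or in analgesia given at discretion, so the report should say which components were assessed masked and which were not.

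### Sections 16-17 assign the arm by an on-site odd/even reading of a random number table, with no concealment, independent holder or prior record; a sealed, logged list would be a cheap improvement

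*Protocol*

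**What the plan says.** Section 16 of the protocol, on sequence generation and implementation, reads "A researcher was assigned to the group by random number method". An odd number means the conventional arm and an even number the arm without a catheter. The section adds "which took place in the operating room". Section 17 gives the source and the timing: "the specific surgical method was determined by random number table method after entering the operating room". The same section says of the patients: "single-blind, the enrolled patients were only told that they could receive either of the two surgical procedures".

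Three other sections bear on the point:

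- Section 15, on who recruits and where: "Recruiting research subjects were conducted by a researcher in the Urology Clinic".
- Section 20: consent covers both procedures.
- Section 8: the allocation ratio may be 1:1 or only roughly so, and the study is called exploratory.

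Sections 8, 11 and 15 to 21 mention no envelope, remote release or other way of hiding the entry. They name no holder of the sequence and no allocation log. The coded identifiers in section 21 are a confidentiality measure, not an allocation record.

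**The concern.** Randomisation protects the comparison only if the person who applies the next assignment can neither foresee it nor set it aside once seen. Section 16 is where a protocol fixes this. It does describe an operating procedure, so this is not a detail left for the statistical analysis plan. As written, the procedure lacks three safeguards: concealment of the entry, an assigner independent of recruitment, surgery and outcome collection, and a record that commits the patient to a number before it is read.

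Without them, a number that points a difficult case to an unwanted arm could be skipped or redrawn. If the table can be read ahead, the order of cases could be changed. Either would put more difficult cases in one arm and shift the complication rate, the primary endpoint, against that arm. Without a log, a skipped number leaves no trace. Because section 8 accepts an approximate ratio, moderately uneven group sizes would raise no question.

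**Working it through.** **Inputs from the protocol.** 100 patients, 50 per group (section 14); odd/even assignment (section 16); chi-squared or Fisher's test for counts, with significance at P < 0.05 (section 19).

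**Assumed inputs.** The protocol gives no complication rate, so these are illustrative: no true effect; 20% of patients are difficult cases; complication risk is 10% in the others and 10% + 25 points in difficult cases; half of the difficult cases drawn to arm A are affected by steering.

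**Step 1. The random source.** Each odd/even draw has probability 1/2, so the size of one arm is Binomial(100, 0.5). P(exactly 50:50) = C(100,50)/2^100 = 0.080. P(more uneven than 45:55) = 0.271. The code is sound, and honest draws often give uneven groups.

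**Step 2. No steering.** Each arm expects 50 patients, 10 of them difficult. Overall risk = 0.10 + 0.20 × 0.25 = 0.15. The SD of the difference is √(2 × 0.15 × 0.85 / 50) = 7.1 points.

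**Step 3. One number skipped once.** The next number gives the same arm half the time, so a difficult case drawn to A ends in B with probability 0.5 × 0.5 = 0.25.
- Difficult cases: A 10 × 0.75 = 7.5; B 10 + 2.5 = 12.5.
- Shares: 7.5/47.5 = 15.8% and 12.5/52.5 = 23.8%.
- False difference: 8.0 × 0.25 = 2.0 points, or 2.0/7.1 = 0.28 SD.

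**Step 4. Every affected patient ends in the other arm.** This needs repeated skipping, reading ahead or overriding the draw.
- Difficult cases: A 5; B 15. Expected split 45:55.
- Shares: 5/45 = 11.1% and 15/55 = 27.3%.
- False difference: 16.2 × 0.25 = 4.0 points, or 0.57 SD.

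By step 1, a 45:55 split would look ordinary.

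**Step 5. Simulation.** 20,000 trials per scenario on the same assumptions; the Monte Carlo error of the Fisher rejection rates is about 0.1 to 0.2 points. The third column is how often a Fisher test would flag the imbalance in difficult cases, if that factor is recorded.

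| Scenario | False difference | Imbalance flagged | Rejection, Fisher | Rejection, chi-squared |
|---|---|---|---|---|
| No steering | 0 | 3.4% | 3.3% | 5.0% |
| One number skipped once | about 2 points | 13% | 4.0% | 5.7% |
| Every affected patient in the other arm | about 4 points | 48% | 6.1% | 8.6% |

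**Step 6. Range for the last row.** With 10-30% difficult cases and 15-25 points extra risk, the false difference runs from 1.4 to 5.4 points, Fisher rejection from 3.5% to 7.9% and chi-squared from 5.4% to 10.3%. With a base risk of 5% or 20%, Fisher rejection is 6.3% or 5.6%.

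**Step 7. The extreme.** If all 10 difficult cases drawn to A were moved, the expected counts are 0/40 against 20/60, a false difference of 33.3 × 0.25 = 8.3 points. The imbalance would be flagged in about 100% of trials, so steering on that scale shows itself if the factor is recorded.

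**The case against.** The strongest case against is that the text already closes the main route to selection bias. Patients are recruited in the clinic, consent to both procedures, and get their arm only after entering the operating room. If the number is drawn fresh at that moment, which section 16 permits, there is no stored next entry to foresee and no reason to reorder cases. A log is also an operational record that a short protocol may leave to other papers, and the study calls itself exploratory. With one skip, Fisher's test stays below 5%.

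Most of this stands, and it limits the point. It does not remove it: a fresh draw cannot be foreseen, but it can be repeated or passed over when nothing binds the patient to it beforehand.

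A reader might infer more than the text supports:

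- That the table lies open, or that someone reads ahead. The protocol says neither.
- That the recruiting and assigning researchers are the same person. Sections 15 and 16 each speak of a researcher without saying so. The awkward wording of section 16 may be a translation slip and may mean a designated allocator.
- That odd/even assignment is not random. Read from a random number table, it is.
- That allocation was in fact subverted. Nothing in the protocol shows this.

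The section 13 flow chart is not available in the text reviewed and could not be checked.

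**Conclusion.** The point holds as a cheap improvement to a stated procedure, not as a demonstrated bias. Sections 16-17 leave the on-site reading without concealment, an independent assigner or a prior record. The remaining risk is a skipped or redrawn number, or reordered cases if the table can be read ahead.

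Its size is modest and depends on how the steering works. Under the assumed inputs, a single skip adds 4.0 − 3.3 = 0.7 points to the false rejection rate with Fisher's test and 5.7 − 5.0 = 0.7 with chi-squared. Moving every affected patient adds 2.8 and 3.6 points. The larger pair should not be quoted for simple skipping, because passing over one number changes the arm only half the time. A baseline check would miss the imbalance in most trials under a single skip and in about half under full movement, and it cannot test a factor that is not recorded.

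**What to change.** In section 16, replace the on-site table reading with a list generated once in advance by a team member not involved in recruitment, surgery or outcome assessment. The odd/even code may be kept. Hold the assignments in sequentially numbered, opaque, sealed envelopes, or use an equivalent concealed release. Open each one in the operating room only after the patient's identifier and eligibility have been written on it, and log every opening.

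If a concealed list is already in use, it is enough to state in section 16 who made it, who holds it and how openings are logged.

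The cost is a few hours of preparation, 100 envelopes and a log sheet. Patients undergo nothing extra, and the arm is revealed at the same moment as now.
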